2.1 Major cardiovascular events

2.1.a. Cardiovascular events will include fatal or non-fatal stroke, coronary events, or revascularization procedures. Stroke will include either ischemic or hemorrhagic. Coronary events will include acute myocardial infarction \pm percutaneous coronary intervention, percutaneous coronary intervention, or coronary artery bypass graft surgery (CABG) surgery. Revascularization procedures include percutaneous coronary intervention, coronary artery bypass graft surgery (CABG) surgery, carotid endarterectomy, interarterial stent insertion. Events will be captured administratively using ICD-9 and/or CPT codes and will be reviewed by individuals blinded the randomization scheme. Cases of fatal or non-fatal strokes will be reviewed and confirmed by a neurologist as will the stroke classification (ischemic, hemorrhagic, or unknown). Coronary event cases will be reviewed by an individual at CPCRS (not associated with the study) who has expertise in validating coronary events. Major cardiovascular events will be evaluated as a combined end point as well as individually.

2.1.b. Hospitalizations: Hospitalizations for any reason will be collected over the study period for all patients.

2.1.c. Death: Death will be captured through KPCO administrative databases. Cause of death will be determined by death certificates and classified as any-cause or cardiovascular. If not cause of death is noted on the death certificate, the cause will be assumed to be cardiovascular. Cardiovascular deaths will include death from cardiac causes, ruptured aortic aneurysm, or peripheral vascular disease. Sudden deaths will be regarded as cardiovascular unless an alternative explanation is documented.

3. Tertiary Outcomes

Tertiary outcome measures will describe the effectiveness and safety of the intervention as compared to Usual care.

.3.1. Lipid and Blood Pressure Control

In addition to evaluating the primary outcome of BP and LDL control at year 3, these parameters will also be evaluated year 1 after randomization. For lipid parameters, in addition to the LDL-C goal attainment, NonHDL goal attainment (<130/ mg/dL) and the LDL/HDL ratio <2.0) will be evaluated at years 1 and year 3. No additional contacts will be made to obtain these readings outside of the intervention/usual care practices. Values available in the medical record \pm 180 days of year 1 will be used for assessing this outcome. If no values are available in this timeframe, just the available data will be analyzed and compared.

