31.0 Hypothesis and Objectives

31.1 Explain the hypothesis and objectives for this study. - For help with this section of the form please click on the help button.

Aim 1: Conduct a randomized, controlled, study of a clinical pharmacist-led disease management intervention for patients with a history of non-cardioembolic ischemic stroke compared to usual care.

Hypothesis 1a: More patients in the clinical pharmacy specialist-led disease management group will achieve their lipid and blood pressure goals compared to the "Usual Care" group.

Hypothesis 1b: Fewer patients randomized to the clinical pharmacy specialist-led disease management group will have recurrent cardiovascular events or death compared to patients in the "usual care" group.

Hypothesis 1c: More patients with ischemic stroke will receive appropriate secondary prevention care using evidence-based medications in the intervention group compared to usual care.

Significance: To our knowledge, this will be the first, prospective, randomized study to evaluate the impact of a clinical pharmacist disease management program on both surrogate and clinical outcomes for patients with non-cardioembolic ischemic stroke.

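### The cardiovascular-death definition omits stroke, contradicting the protocol's own event definition, and the protocol does not say whether the combined end point includes death

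*Protocol*

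**What the plan says.** The relevant text is in Protocol section 33.0, under the secondary outcome headed 2.1 Major cardiovascular events, and in section 31.0.

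- **Events (2.1.a).** "Cardiovascular events will include fatal or non-fatal stroke, coronary events, or revascularization procedures". The coronary component is then spelled out: "Coronary events will include acute myocardial infarction", with or without percutaneous coronary intervention (PCI), or PCI or bypass surgery (CABG) alone. Fatal and non-fatal strokes go to a neurologist for confirmation and typing. On analysis: "Major cardiovascular events will be evaluated as a combined end point as well as individually".
- **Death (2.1.c).** "Cause of death will be determined by death certificates and classified as any-cause or cardiovascular". The cardiovascular category is defined by a list: "Cardiovascular deaths will include death from cardiac causes, ruptured aortic aneurysm, or peripheral vascular disease". Two default rules extend it. Where the certificate gives no cause, "the cause will be assumed to be cardiovascular". And "Sudden deaths will be regarded as cardiovascular unless an alternative explanation is documented".
- **Hypothesis 1b (31.0).** Fewer intervention patients than usual-care patients "will have recurrent cardiovascular events or death".

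Stroke or cerebrovascular death appears neither in the 2.1.c list nor in its default rules.

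**The concern.** The trial tests secondary prevention after ischemic stroke, so stroke death is a central cause of death to classify correctly. As written, the cardiovascular-death outcome takes in deaths whose cause nobody recorded and leaves out deaths certified as stroke. The same fatal stroke is a cardiovascular event under 2.1.a and not a cardiovascular death under 2.1.c. Anyone applying the rules literally would report a wrong cardiovascular-death count, and two coders could disagree on the same certificate.

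Hypothesis 1b has a related problem. It speaks of events or death, but the combined end point is mentioned only within the event definition, with no statement on whether death belongs to it. If the choice is made after the groups have been compared, the 1b result is open to challenge.

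**Working it through.** This is a question of definitions, so the main check is to run each type of death through the rules as written.

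| Type of death | 2.1.a composite | 2.1.c cardiovascular death | Any-cause death |
|---|---|---|---|
| Certified stroke | Counted (fatal stroke) | **Not listed** | Counted |
| Fatal myocardial infarction | Counted (acute infarction, not limited to non-fatal) | Counted (cardiac) | Counted |
| Cardiac or sudden death, no coded infarction or procedure | **Not counted** | Counted | Counted |
| No cause on certificate, no coded event | Not counted | Counted by default | Counted |
| Ruptured aortic aneurysm or peripheral vascular disease, no coded event | Not counted | Counted | Counted |

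Row 1 is the contradiction. Comparing rows 1 and 4 shows that, within cardiovascular death, an unknown cause is in and a known stroke is out. Row 3 is the reverse gap: 2.1.c calls the death cardiovascular, but the 2.1.a composite does not see it.

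**Hypothesis 1b.** If the combined end point is 2.1.a alone, the deaths in rows 3 to 5 do not count towards it. If it includes any-cause death, all rows count. The protocol does not say which applies.

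**Effect on the primary outcome.** The only sample-size figure in the protocol rests on reaching blood pressure and LDL-C goals: 45% versus 60%, two-sided alpha 0.05, power 80%. With pooled proportion 0.525:

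n = [1.960 × √(2 × 0.525 × 0.475) + 0.842 × √(0.45 × 0.55 + 0.60 × 0.40)]² / 0.15² = (1.384 + 0.588)² / 0.0225 ≈ 173 per group.

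This reproduces the stated 173. No death or event rate enters it, so correcting the definitions changes neither sample size nor power.

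**How many deaths are affected.** The protocol gives no share of deaths due to stroke and no stroke fatality, so only a range under assumptions is possible.

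- Via total deaths: the background (section 30.0) cites 9.1% per year, so 400 × (1 − 0.909³) = 99.6, about 100 deaths in 3 years. An assumed 2% per year gives 400 × (1 − 0.98³) = 23.5. With an assumed stroke share of 5% to 30%, that is about 5 to 30 deaths at the higher rate and about 1 to 7 at the lower.
- Via recurrent strokes: the background cites 4% per year, so 400 × (1 − 0.96³) = 46 strokes. With an assumed fatality of 15% to 25%, that is 6.9 to 11.5 deaths.

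Both routes give all 400 patients three full years. The protocol expects about 20% dropout and ends follow-up at plan termination, a first cardiovascular event or death (section 45.1). The 4% applies after the first year, whereas any stroke within 5 years qualifies for entry. These figures therefore show scale only and are not estimates.

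**The case against.** The best defence is that the wording of 2.1.c need not be exhaustive. The sentences around the list already add sudden deaths and deaths of unstated cause, and a sensible coder would include stroke. But 2.1.a uses the same construction to define the composite, and the list is detailed enough to name aneurysm and peripheral vascular disease. The background also refers to cardiovascular disease other than stroke, which implies that the term normally covers stroke. The defence makes the error less likely to take effect, but does not remove the contradiction.

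It can also be said that details of a combined end point belong in a statistical analysis plan. That is fair for analysis method, but here the protocol itself fixes the definitions, and they conflict.

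Other objections stand, and they limit the point. A reader might infer any of the following, none of which the protocol supports:

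- *Stroke deaths are treated as non-cardiovascular throughout.* They count in the 2.1.a composite and in any-cause death, and no comparison of non-cardiovascular deaths is planned.
- *Fatal coronary disease leaves a patient event-free.* A fatal infarction enters as acute myocardial infarction. Only cardiac or sudden death without a coded infarction or procedure escapes.
- *Hypothesis 1b has no matching outcome.* Events and any-cause death are both listed and each can be tested. What is missing is a stated combination.
- *PCI and CABG are double counted.* They appear under two components, but outcomes are scored yes or no per patient, so the composite cannot count them twice. Overlap between component tables is ordinary.
- *The treatment effect is diluted or reversed.* The same rule applies to both arms, and no calculation shows either result.

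**Conclusion.** The point holds, at moderate severity. Item 2.1.c, applied as written, leaves certified stroke deaths out of cardiovascular death and contradicts 2.1.a. The misclassification is confined to that one category. Separately, the composite misses cardiac or sudden death without a coded infarction or procedure, and the role of death in the combined end point for hypothesis 1b is unstated.

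Only secondary outcomes are touched. The conclusion about the definitions rests on a literal reading of the list and on no numerical assumption. The number of deaths misclassified cannot be derived from the protocol. In particular, the 7 to 12 deaths obtained from the recurrence rate depend on an assumed fatality share and on complete follow-up of 400 patients, and should not be read as a finding.

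**What to change.** 1. In 2.1.c, add stroke (ischemic, hemorrhagic or unknown type) to the causes that make a death cardiovascular, so that it agrees with 2.1.a.
2. State that the combined end point for hypothesis 1b is a cardiovascular event as defined in 2.1.a or death from any cause, counted once per patient. This closes the gap for cardiac and sudden deaths without a coded event and fits the planned yes/no comparison of proportions. A change to time-to-event analysis is not needed for this purpose.
3. Report the 2.1.a composite, any-cause death and cardiovascular death separately as well.

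The cost is a few lines of wording. Death certificates and the neurologist's review are already planned and supply the data. The one drawback is that secondary definitions change after they were written, so the change should be documented and made before group comparisons are seen.

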3.2. Evidence-Based Medications

3.2.a. Antiplatelet/Antithrombotic Medications: Prescriptions for antiplatelet therapy (dipyridamole/aspirin, ticlopidine, clopidogrel and/or prasugrel) or anticoagulation therapy (warfarin) will be assessed at 1 and 3 years after randomization for both groups. Patients will be considered persistent to these medications if days supply/sold date (\pm 15 days) overlaps the date of the 1 and 3 year timeframes. Aspirin use will only be collected by patient report at baseline and at 3 years for both groups. This is an over-the-counter medication that is not tracked in the KPCO prescription databases. The only way to capture ASA data will be through patient report.

3.2.b Antihyperlipidemic Medications: In addition to lipid goal attainment, the prescription antihyperlipidemic medications and dose the patient is taking will be collected at 1 and 3 years for both groups. The medications will be classified as statin, fibric acid derivatives, ezetimibe, nicotinic acid (i.e. Niaspan®), bile acid sequestrants, or other. Patients will be considered persistent to the lipid-lowering therapy if the days supply overlaps the date (\pm 15 days) of their FLP result at each time point.

3.2.c. Antihypertensive Medications: In addition to blood pressure goal attainment, the antihypertensive medications and dose the patient is taking will be collected at each time point (1 and 3 years). Medications will be classified into therapeutic classes (i.e. thiazide diuretic, ACE inhibitor, β -blocker, calcium channel blocker, etc). Patients will be considered to be persistent to antihypertensive therapy if the days supply (\pm 15 days) overlaps the date of their blood pressure assessment.

3.3. Smoking Cessation: Smoking cessation will be assessed for both groups at baseline and study end (year 3) per patient report and will be coded as current, past (quit 5 years ago), or never. Smoking will include any nicotine products (cigarettes, cigars, pipes) and chewing tobacco. The quantity smoked or second-hand smoke exposure will not be captured.

Sample Size Calculation

For the primary outcome of proportion at both BP and LDL-c goals at year 3, and based on prior studies,²⁸ we estimate that 45% of patients in the Usual Care group will meet the end point at 3-years and conservatively estimate that 60% the CPCRS intervention will meet the end point. An enrollment number of 173 patients per group will be required, with a two-sided alpha of 0.05 and power of 80%. To account for about a 20% dropout rate, the number will be inflated to 200 patients per group.

It is estimated that approximately 5200 patients will have validated stroke, of which

4200 will have ischemic stroke (both cardioembolic and non-cardioembolic and approximately 2500 will have non-cardioembolic ischemic stroke. We anticipate that with this pool of patients, we should be able to meet this sample size calculation.

Statistical Analysis

All statistical analyses will be performed on an intention-to-treat basis utilizing SAS (SAS, Cary, NC) statistical software. Baseline subject characteristics for each study group will be reported as means, medians, and standard deviations for interval- and ratio-level variables (e.g., age, length of time between events, mean lipid levels) and percentages for nominal- and ordinal-level data (e.g., sex, cardiovascular event history). All patients who completed follow-up in their randomized intervention assignment at years 1 and years 3 (as outlined in outcomes assessment) will be included regardless of whether they interacted with CPCRS or not. Interval-level outcome variables will be assessed for normality of their distributions and appropriate tests (e.g., t-test, rank-sum test) will be used to assess differences in mean values between groups. Study outcomes will be dichotomized as yes/no (e.g., reached BP & LDL goal levels yes/no, persistent

with lipid-lowering therapy yes/no). To assess differences in proportions between groups on dichotomous outcome variables, Pearson's chi-square test of association will be utilized. An alpha < 0.05 will be considered statistically significant.

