Intervention (CPCRS) Group: The intervention will utilize clinical pharmacy specialists in CPCRS. The intervention will be similar to what is applied to patients with CAD. CPCRS will ensure patients have regular laboratory monitoring (i.e. lipids) and blood pressure measures, initiated on appropriate lipid-lowering and antihypertensive medications, and receive follow-up in a timely manner. CPCRS staff will order evidence-based lipid-lowering and/or antihypertensive medications, adjust doses, and order follow-up laboratory parameters, as necessary under pre-approved regional treatment protocols (Appendix V). Patients will be monitored for medication adherence and adverse effects. Patients receive dietary, exercise, and smoking cessation counseling verbally and through mailing of pre-printed Kaiser Permanente approved, patient education pamphlets, as necessary per the discretion of the clinical pharmacy specialist. Patients requiring more intensive dietary counseling will be referred to dietitians, education classes, or other appropriate resources offered at KPCO. Primary care providers will be informed of all medication initiations or

dosage adjustments via documentation in the electronic medical record. Any clinical scenarios that the clinical pharmacy specialist is unclear on how to proceed will have requests for consultation of either the PCP, neurologist or the CPCRS medical director. The primary mode of communication between CPCRS and patients will be via telephone or e-mail through kp.org. Patients who achieve their lipid and blood pressure treatment goals will be placed into long-term "CPCRS-maintenance" which will require less intensive CPCRS management. Patients will have laboratories and blood pressure checked annually per regular treatment protocols, until study end.

Usual Care: Patients randomized to Usual Care will continue to receive interventions/procedures they normally receive according to standard/usual care practices.

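### The ±15-day window for lipid-lowering persistence also counts drugs first filled after the lipid result, and may distort the comparison between arms in either direction

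*Protocol*

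**What the plan says.** Section 3.2 of the protocol (Evidence-Based Medications, among the tertiary outcomes under 33.0 Data Analysis) defines persistence three times, and the wording differs each time.

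- **3.2.b, lipid-lowering drugs:** "Patients will be considered persistent to the lipid-lowering therapy if the days supply overlaps the date (\pm 15 days) of their FLP result at each time". The tolerance belongs to the date of the lipid result.
- **3.2.c, antihypertensives:** "Patients will be considered to be persistent to antihypertensive therapy if the days supply (\pm 15 days) overlaps the date of their blood pressure assessment". The tolerance belongs to the supply, and the anchor is the blood pressure (BP) date.
- **3.2.a, antiplatelet and antithrombotic drugs:** the supply or sale date, with the same 15 days, "overlaps the date of the 1 and 3 year timeframes". The anchor is a calendar date.

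None of the three asks that the drug was dispensed before the anchor date.

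The Statistical Analysis text in 33.0 gives persistence with lipid-lowering therapy as an example of a yes/no outcome, to be compared between groups by Pearson's chi-square test at the 0.05 level. The related hypothesis is 1c in section 31.0: "More patients with ischemic stroke will receive appropriate secondary prevention care using evidence-based medications in the intervention group compared to usual care".

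Section 45.1 describes the intervention: "CPCRS staff will order evidence-based lipid-lowering and/or antihypertensive medications, adjust doses, and order follow-up laboratory parameters, as necessary". Usual Care patients simply go on with their normal care.

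**The concern.** Persistence at a lipid result should mean that the patient had the drug when the blood was drawn. Under 3.2.b, someone who had no statin at the time, and who filled a prescription six days later because the LDL-C was high, is recorded as persistent at that measurement. The rule mixes drug use at the assessment with the reaction to the assessment.

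This misclassification need not be equal in the two arms. The anchor is the kind of result that CPCRS pharmacists act on under treatment protocols, and usual care has no such service. If fills after the result are more or less common in one arm, the chi-square comparison of persistence shifts even when the true share on drug is the same. A real difference can likewise be enlarged or reduced.

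**Working it through.** **Does a later fill count?** Take a patient with no supply at the result and a first fill on day +6.

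- 3.2.b: the window runs from day -15 to day +15, and supply begins on day +6. They overlap, so the patient is scored persistent.
- 3.2.c, first reading (the supply interval is widened by 15 days at both ends): supply begins on day +6 - 15 = day -9, so it covers day 0. The patient is scored persistent.
- 3.2.c, second reading (the tolerance is only a grace after run-out): supply begins on day +6 and cannot reach back to day 0. The patient is scored not persistent.
- 3.2.a: a later fill can fall inside the window, but the anchor is a calendar date, so no lipid or BP result prompts the fill.

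**Size.** The protocol has no persistence figure to reproduce. Its one computed figure, 173 per group for the primary outcome (45% v 60%, two-sided alpha 0.05, 80% power), reproduces as 173 and plays no part here.

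Inputs:

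- *p*, the true share covered at the result, is assumed.
- *s*, the share of uncovered patients who fill within 15 days after the result, is assumed.
- *n* = 200 × (1 - 0.20) = 160 per arm, from the planned enrolment and dropout in the Sample Size Calculation.

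With C for CPCRS and U for Usual Care:

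- observed persistence = *p* + (1 - *p*)*s*
- artefact = (1 - *p*C)*s*C - (1 - *p*U)*s*U

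| True coverage C v U | Starts after result C v U | Observed C v U | True difference | Artefact (points) |
|---|---|---|---|---|
| 70% v 70% | 40% v 20% | 82% v 76% | 0 | +6 |
| 70% v 70% | 50% v 10% | 85% v 73% | 0 | +12 |
| 90% v 90% | 40% v 20% | 94% v 92% | 0 | +2 |
| 70% v 70% | 20% v 20% | 76% v 76% | 0 | 0 |
| 80% v 70% | 40% v 20% | 88% v 76% | +10 | +2 |
| 80% v 70% | 30% v 20% | 86% v 76% | +10 | 0 |
| 80% v 70% | 20% v 20% | 84% v 76% | +10 | -2 |

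First row: 0.70 + 0.30 × 0.40 = 0.82 and 0.70 + 0.30 × 0.20 = 0.76. Last row: 0.80 + 0.20 × 0.20 = 0.84 and 0.70 + 0.30 × 0.20 = 0.76, so a true +10 is seen as +8.

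In the first three rows true persistence is equal. By the normal approximation with 160 per arm, a two-sided 5% test would reject in about 26%, 75% and 11% of trials.

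**Direction.** The artefact favours CPCRS only if *s*C/*s*U exceeds (1 - *p*U)/(1 - *p*C):

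- coverage 80% v 70%: 0.30/0.20 = 1.5
- coverage 85% v 70%: 0.30/0.15 = 2.0
- coverage 90% v 70%: 0.30/0.10 = 3.0

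**After the fix.** If fills dispensed after the result do not count, observed persistence equals *p* in each arm. The artefact is zero, and the rejection rate under equal persistence returns to 5%.

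**The case against.** A reader might infer four stronger things, and the protocol does not support them.

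1. *The window favours CPCRS.* This is plausible, because acting on results is part of the intervention. But no start rate after a result is given for either arm. If CPCRS improves coverage, fewer of its patients are uncovered at the result, and similar start rates then shrink its advantage.
2. *All three definitions share the fault.* In 3.2.a no result prompts the fill, and section 45.1 names only lipid-lowering and antihypertensive drugs in the sentence on CPCRS ordering. In 3.2.c the tolerance can fairly be read as a run-out grace. Only 3.2.b is clear.
3. *The bias is 4 to 11 points.* That follows from 60% coverage in both arms, 50% to 70% of uncovered patients above goal, and fills of 30% to 50% v 10%: 0.4 × 0.5 × 0.2 = 0.04 and 0.4 × 0.7 × 0.4 = 0.112. It assumes equal coverage after an intervention meant to raise it, and a three- to fivefold difference in fills. With coverage of 80% v 70% and the rest unchanged, the range is 1.5 to 4.9 points (0.2 × 0.5 × 0.3 - 0.3 × 0.5 × 0.1 = 0.015; 0.2 × 0.7 × 0.5 - 0.3 × 0.7 × 0.1 = 0.049).
4. *Hypothesis 1c is undermined.* It concerns receiving appropriate drugs, and a drug started at the assessment is arguably such care, even if persistence is the wrong name for it. Section 3.2 also collects drugs and doses at 1 and 3 years. Nor does the protocol plan to relate persistence to the LDL-C or BP value; it describes comparisons between groups only.

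A further objection is that this tier merely describes: "Tertiary outcome measures will describe the effectiveness and safety of the intervention as compared to Usual care". That carries less weight, because the analysis text names lipid-lowering persistence as a yes/no outcome for the chi-square test. All four limits stand. They leave intact that 3.2.b, as written, records some patients as persistent who had no drug at the result.

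**Conclusion.** The point holds for 3.2.b, and for 3.2.c on one reading. A lipid-lowering drug first filled or restarted within 15 days after the lipid result, possibly because of it, counts as persistence at that result. Since only one arm has a service that orders drugs in response, the error may differ by arm.

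The protocol settles neither sign nor size. The illustrations above run from -2 to +12 points. The upper end needs equal coverage and a fivefold difference in start rates; the negative value needs better CPCRS coverage with equal start rates. All coverage and start rates are assumptions.

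The reach is limited. Only patients without drug on hand at the result can be misclassified, because a dose change in a covered patient does not alter the yes/no answer. The outcome is tertiary, and the primary outcome (LDL-C and BP goals at 3 years) and the cardiovascular events are untouched. It is a cheap correction worth making, not a threat to the trial's main conclusion.

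**What to change.** In 3.2.b and 3.2.c, define a patient as persistent if a fill dispensed on or before the FLP or BP date has a days supply that, with a 15-day grace after run-out, reaches that date. State that fills first dispensed after the result do not count; they may be reported separately as post-result starts. This also removes the ambiguity in 3.2.c. Use the same wording in 3.2.a, with the 1- and 3-year dates as anchors, for consistency only.

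The change uses the same pharmacy data and needs no new collection. Its cost is that stated persistence may be slightly lower in both arms, because a patient whose supply ran out more than 15 days before the result and who refilled soon after it would no longer count. It removes the artefact whichever way it would have gone.

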32.0 Study Methods

32.1 Provide a description of how the study question (hypothesis) will be tested and how participants or their health information will be involved in the study.

For help with this question please click on the help button.

Study Design: This will be a randomized, controlled study comparing a clinical pharmacist-led disease management intervention by the Clinical Pharmacy Cardiac Risk Service (CPCRS) to usual care (UC). Randomization will be 1:1 and will occur at the patient-level.

Patient Selection Criteria

Inclusion Criteria:

All active KPCO non-institutionalized patients from the Denver/Boulder metropolitan area with a validated non-cardioembolic ischemic stroke diagnosis within the past 5 years who:

- § Are ≥ 18 years of age at the time of informed consent, and
- § Are Eligible for CPCRS enrollment, and

§ Have uncontrolled blood pressure (the most recent value >130/80 mmHg noted in the medical record), and/or

§ Have last LDL-C, within the previous 365 days, that is ≥ 100 mg/dL (the most recent will be used).

Exclusion Criteria:

Patients will be excluded if:

§ → >85 years of age at the time of consent,

§ Have transient ischemic attacks, subarachnoid hemorrhage, intracerebral hemorrhage, or cardioembolic stroke as their only validated stroke history,

§ Die within 30 days of stroke,

§ Are already followed by the Clinical Pharmacy Cardiac Risk Service (CPCRS). These patients either have a history of coronary artery disease (acute MI, CABG, percutaneous coronary interventions, and/or coronary catheterizations), are at high-risk for CAD as determined by the cardiologist, or have peripheral arterial disease,

§ Have a diagnosis of dementia or a terminal illness in which the life expectancy is <3 years per the discretion of the primary care provider,

§ Have notation in the medical record of memory issues or other conditions which, based on the judgment of study staff, suggest that the patient may not be able to provide informed consent,

§ Are pregnant or breast-feeding, or

§ Do not consent to participate

§ Currently listed on the "Do Not Call List"

Both English and Spanish speaking patients will be eligible for participation.

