36.0 Enrollment

36.1 Estimated number of participants:

Within KPCO:

400

Total all sites:

400

Comments:

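### Allowing for 20% dropout takes 173 per group to 217, not 200; at that dropout rate the trial has about 77% power, not the stated 80%

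*Protocol*

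**What the plan says.** The sample size paragraph in section 33.0 of the protocol concerns the primary outcome, the proportion of patients at both LDL-C and blood pressure goals at year 3. Its inputs are:

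- Usual care: "we estimate that 45% of patients in the Usual Care group will meet the end point at 3-years".
- Intervention: "conservatively estimate that 60% the CPCRS intervention will meet the end point".
- Base size: "An enrollment number of 173 patients per group will be required", at two-sided alpha 0.05 and 80% power.
- Allowance for loss: "To account for about a 20% dropout rate, the number will be inflated to 200 patients per group".

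Allocation is equal (section 32.0: "Randomization will be 1:1 and will occur at the patient-level"). Section 36.1, under "Estimated number of participants", gives 400 in total, so 200 per group is the operative target and not a slip in one place. The statistical analysis paragraph of section 33.0 names the Pearson chi-square test for dichotomous outcomes. It declares an intention-to-treat basis, and then describes the included patients as those who completed follow-up in their assigned group.

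**The concern.** The paragraph gives a required number, a dropout rate and an enrolment target, and the three do not fit together. Taking 20% off 200 leaves fewer patients than the same paragraph says are required. The stated 80% power is therefore not the power of the trial under its own assumptions.

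The paragraph is the only justification for enrolling 400, and a reader weighing a non-significant primary result would take 80% as the design power. Loss is also a realistic prospect. The outcome falls at 3 years and needs both an LDL-C and a blood pressure value within 60 days either side of the study end date. Section 45.1 also ends follow-up at plan termination, a first cardiovascular event or death, and the protocol does not say whether the 20% includes these.

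**Working it through.** **Inputs** (section 33.0 unless noted): p₁ = 0.45, p₂ = 0.60, so p̄ = 0.525 and the difference is 0.15; z for two-sided 0.05 = 1.960; z for 80% power = 0.842; 1:1 allocation (section 32.0); Pearson chi-square test, no continuity correction stated; dropout 20%; 200 enrolled per group.

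**Step 1: reproduce the base size.** Pooled two-proportion formula:

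n = [1.960·√(2p̄(1−p̄)) + 0.842·√(p₁(1−p₁) + p₂(1−p₂))]² / (p₂−p₁)²

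- √(2 × 0.525 × 0.475) = 0.7062, and × 1.960 = 1.3842
- √(0.2475 + 0.2400) = 0.6982, and × 0.842 = 0.5876
- n = (1.3842 + 0.5876)² / 0.15² = 172.8, so **173 per group**

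This matches the protocol exactly. The arcsine method also gives 173, the unpooled formula 171 and the continuity-corrected formula 186. The base figure is sound, and the error lies only in the next step.

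**Step 2: inflate for 20% dropout.**

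| Rule | Calculation | Per group |
|---|---|---|
| Correct, n/(1−d) | 173/0.80 = 216.25 | 217 |
| Common shortcut, n(1+d) | 173 × 1.2 = 207.6 | 208 |
| Protocol | – | 200 |

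Neither rule gives 200.

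**Step 3: what 200 covers.** The largest loss that still leaves 173 is 1 − 173/200 = 13.5%. As a multiplier, 200/173 is an increase of 15.6%. A 15% dropout rate would already need 173/0.85 = 203.5, so 204.

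**Step 4: power at the protocol's own dropout rate.** Evaluable patients: 200 × 0.80 = 160 per group, which is 173 − 160 = 13 too few.

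Power = Φ[(0.15·√160 − 1.3842)/0.6982] = Φ[(1.8974 − 1.3842)/0.6982] = Φ(0.735) = **76.9%**

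| Evaluable per group | Power by formula | Exact power of the chi-square test |
|---|---|---|
| 160 | 76.9% | 77.0% |
| 173 | 80.0% | 79.2% |
| 200 | 85.4% | 85.6% |

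**Step 5: sensitivity to how dropouts are handled.** The 76.9% assumes that dropouts leave the analysis. If they were instead counted as not at goal (an assumption, not in the protocol), the rates become 0.8 × 45% = 36% and 0.8 × 60% = 48%. Power with all 200 per group is then about 68%.

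**The case against.** The arithmetic is not in dispute, and nothing elsewhere in the protocol repairs it. The case on the other side is about weight and conditions.

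- **The effect is small.** The loss is about 3 points of power, well inside the uncertainty of the inputs: with 160 per group, an intervention rate of 60.6% instead of 60% gives 80.1% power. A null result would in any case be judged by its confidence interval. This stands, and it limits the seriousness of the point.
- **The dropout rate is only approximate.** The protocol does qualify the 20%. But 200 covers no more than 13.5%, which is too far from 20% to pass as rounding.
- **Dropouts may not be lost to the analysis.** The protocol declares intention-to-treat and takes outcomes from routine records, backed by two reminder letters and a call, so a patient who stops contact with the service may still have the outcome. Dropout is not defined. This stands in part: 77% is conditional on losing the outcome for 20%. But the protocol's own inflation makes sense only if dropouts reduce the analysed number, and counting them as failures would lower the power further.
- **The 45% is itself doubtful.** The background (section 30.1) reports, from the reference cited for the 45%, 45.3% at blood pressure target and 19.4% at lipid target in cerebrovascular patients, so the proportion at both could not exceed 19.4% in that source. The same 15-point difference from 19.4% would need about 136 per group, and 160 would give about 86% power. This is a fair but separate question. It does not make 200 the right inflation of 173.

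**Conclusion.** The point holds. The protocol's 173 is right, and its inflation to 200 is wrong for a 20% dropout rate. At that rate the target is short by 13 evaluable patients per group, or 217 − 200 = 17 enrolled per group (34 in total). Power is about 77% instead of 80%, so the type II error is about 23% instead of 20%.

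This rests on 45% versus 60%, the uncorrected chi-square test, and dropouts being left out of the analysis. It is a modest error: it does not bias the estimate, change the type I error or undermine the design. It still needs correcting, because it misstates the power for the primary outcome and can be shown to be wrong from the paragraph's own figures.

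**What to change.** Keep 400 patients and replace the inflation sentence with one that says:

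> With 200 patients per group and 20% dropout, 160 per group are evaluable, and power is about 77% to detect 45% versus 60% at two-sided alpha 0.05, with dropouts excluded from the analysis. Power of 80% is retained only if dropout is at most 13.5%.

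The cost is one corrected sentence and a slightly less favourable stated power. The design, endpoint, test and enrolment stay the same. Keeping 80% power at 20% dropout would instead take 217 per group, 434 in total, but that is not requested.
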